6.7.1 Electrocardiogram (ECG)

Baseline, post-dose, and change from baseline for ECG parameters (heart rate (HR), RR interval, QRS interval, PR interval, QT interval, and QTcF) along with clinically significant abnormalities on T and U waves will be presented by cohort and overall. Triplicate ECGs will be conducted on Day 1 (at pre-dose, 90 minutes post-dose, and 8 hours post dose) and single ECGs at other timepoints. Results will also be listed by subject ID.

Clinically significant findings will be presented based on the following categories:

- The proportion of patients obtaining a heart rate change from baseline > 25% decrease resulting in a heart rate < 50 beats per minute (bpm) and heart rate change from baseline > 25% increase resulting in a heart rate > 100 bpm.
- The proportion of patients obtaining a QRS change from baseline > 25% increase resulting in QRS > 120 ms.
- The proportion of patients obtaining a PR interval change from baseline > 25% increase reaching a value of > 220 ms.
- The proportion of patients obtaining a QTcF increase from baseline values > 30 ms and ≤ 60 ms; and > 60 ms.
- The proportion of patients obtaining treatment emergent absolute QTcF values > 450 ms and ≤ 480 ms; > 480 ms and ≤ 500 ms; and > 500 ms.

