1.3 SCHEDULE OF ACTIVITIES (SoA)

Table 1 Schedule of Activities (Subjects with Neurodegenerative Diseases, All Dose Cohorts)

Study Procedures	Screening ¹	Treatment	Follow-up	Notes
Study Visit	-42 to -1	Day 1	Day 8/EOS/ET	
Visit window (days)	42		+2	
Informed consent	X			
Domiciled		X ^a		a. Subjects will be admitted to the clinical research unit in the morning for 8 hours confinement
Medical/ocular history/Physical exam	X			On Day 1, PE may be repeated if abnormalities are detected at screening. Relevant ocular and disease-specific history will be captured up to date of diagnosis.
Eligibility (inclusion/exclusion criteria)	X			
Body weight and Height	X			
Eye examination/	X	X	X	Refer to Section 8.1.1.
Color fundus photography	X			
Vital signs	X	X ^b	X	b. To be collected predose, and at 0.25, 0.5, 1, 2, 8 hours postdose. A window of \pm 5 minutes will be allowed for measurements up to 2 hours, and \pm 10 minutes beyond 2 hours.
12-lead safety (ECG)	X	X ^c	X	c. Triplicate at the following timepoints: predose (within 1 hour), and at 90 minutes (\pm 15 minutes) and 8 hours (\pm 60 minutes) postdose or before discharge
Safety laboratories	X	X ^d	X	Refer to Section 10.2. d. To be collected predose on Day 1 and before discharge
Urinalysis	X	X	X	
Pregnancy test	S	U (predose)	U	S = Serum; U = Urine
Adverse event reporting	X	X	X	

Study Procedures	Screening ¹	Treatment	Follow-up	Notes
Study Visit	-42 to -1	Day 1	Day 8/EOS/ET	
Visit window (days)	42		+2	
Concomitant medications	X	X	X	
Retinal fundus fluorescence (FF) imaging		X ^e	X	e. Refer to Section 8.1.2
Retinal optical coherence tomography (OCT) and OCT angiography (OCTA)	X		X	
Blood PK sampling		X ^f		f. On Day 1, PK blood samples will be collected at the following time points: 0 (predose), and at 3, 6, 15, and 30 minutes postdose and 1, 2, 4, 6, and 8 hours postdose. A window of ± 5 minutes will be allowed for samples collected from 30 minutes to 2 hours, and ± 10 minutes beyond 2 hours.
Study drug administration		X		

Abbreviations: AE, adverse events; ECG, electrocardiogram; EOS, end of study; ET, early termination; FU, follow-up; PE, physical examination; PK, pharmacokinetics.

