The safety of AMDX-2011P has been evaluated in a program of Good Laboratory Practice (GLP) toxicology and safety pharmacology studies, conducted using a single bolus IV injection of AMDX-2011P to mimic the clinical dosing regimen. In the definitive GLP single-dose rat study, no adverse target organ toxicity and no evidence of ocular or cutaneous phototoxicity were identified at up to 50 mg/kg. Injection site reactions occurred in rats after administration into the tail vein, which were considered adverse at 50 mg/kg and not adverse at \leq 15 mg/kg. Therefore, in rats, the dose showing no adverse systemic toxicity was 50 mg/kg, and the overall study no-observed-adverse-effect level (NOAEL) was 15 mg/kg. In safety pharmacology studies conducted in rats, there were no acute neurobehavioral changes or effects on respiratory function at up to 50 mg/kg. In the definitive GLP single-dose dog study, reversible clinical ophthalmic signs, including mydriasis, minimal hyperemic conjunctiva and minimal to mild chemosis, occurred in male dogs within 24 hours postdose at 60 mg/kg. Other non-adverse clinical signs at 60 mg/kg included intermittent emesis and soft feces, which resolved by Day 2 and were not considered adverse. There was histologic evidence of injection site reactions in dogs at all doses, which were not considered adverse. There was no adverse target organ toxicity in dogs at 60 mg/kg, which was considered the NOAEL in females; the NOAEL in males was 20 mg/kg.

based on ophthalmic changes at 60 mg/kg. In a dog cardiovascular safety study, transient reductions in blood pressure (systolic, diastolic, and mean arterial pressure) and heart rate occurred at 15-30 minutes after a single bolus injection of 30 mg/kg, but not at \leq 10 mg/kg, and there were no effects on electrocardiogram (ECG) profile at any dose. In vitro, AMDX-2011 caused a dose-dependent inhibition of the human Ether-à-go-go-related gene (hERG) cardiac potassium channel of up to 44% at a concentration of 10 μ M. This concentration is expected to be at least 10-fold above human peak plasma concentration (C_{max}) values of the pharmacologically relevant doses; therefore, a risk for QTc prolongation in humans is considered low. Overall, the nonclinical safety studies support the safe administration of AMDX-2011P in this study.

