2.3.1 Known Potential Risks

This is the first-in-human (FIH) study with AMDX-2011P. Though similar and higher doses of AMDX-2011P have been tested in multiple animal studies and results support the dose level to be tested in humans, this will be the first clinical exposure of the study drug; thus, there may be risks that are currently unknown.

There are no identified or potential risks of particular severity or seriousness anticipated on the basis of the mechanism of action of AMDX-2011P. The potential risks are based on theoretical considerations and findings ([Table 2](#)) from completed GLP nonclinical safety studies.

Table 2 Risk Assessment

Potential Risk of Clinical Significance	Summary of Data/Rationale for Risk	Mitigation Strategy
Potential Risks which may be associated with Study Drug		
Phototoxicity	Both AMDX-2011P and AMDX-2011 were suspected of being phototoxic in the in vitro	Subjects will be instructed to avoid direct sunlight and wear

Potential Risk of Clinical Significance	Summary of Data/Rationale for Risk	Mitigation Strategy
	3T3 neutral red uptake phototoxicity test; however, there was no evidence of ocular or cutaneous phototoxicity after IV administration of AMDX-2011P to pigmented rats at doses of up to 50 mg/kg followed by exposure to ultraviolet B, ultraviolet A, and visible light from a xenon lamp.	protective gear (e.g., sunglasses) for 24 hours after dosing. Ophthalmologic examinations will be conducted throughout the study.
Effect on eye	In male dogs, single IV bolus injections of 60 mg/kg AMDX-2011P resulted in mydriasis, minimal hyperemic conjunctiva and minimal to mild chemosis within 24 hours postdose, which was reversible within 6 days.	Ophthalmologic examinations will be conducted throughout the study.
Effect on cardiovascular function	In dogs, single IV bolus injections of 30 mg/kg AMDX-2011P resulted in transient reductions in systolic, diastolic, and mean arterial pressure and heart rate 15-30 min after injection. In vitro, inhibition of hERG channel was seen at high concentrations of AMDX-2011P.	Vital sign assessments, triplicate ECG recording

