6.7.3 Vital Signs

Vital signs assessment include systolic blood pressure (mmHG), diastolic blood pressure (mmHG), temperature (F), heart rate (beats/min), and respiration (per/minute) for each protocol specified timepoint.

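### The SAP's only heart-rate event categories use ECG readings that start at 90 minutes, so the vital signs covering the 15-30 minute risk window have no pre-specified event rate

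*SAP*

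**What the plan says.** **The risk.** On the dog cardiovascular work, Protocol 2.1 reports that "transient reductions in blood pressure (systolic, diastolic, and mean arterial pressure) and heart rate occurred at 15-30 minutes after a single bolus injection". The dose that produced this was 30 mg/kg; nothing similar was seen with 10 mg/kg or less. Table 2 (Protocol 2.3.1) carries this forward as a potential risk: the injections "resulted in transient reductions in systolic, diastolic, and mean arterial pressure and heart rate 15-30 min after injection". The mitigation it gives is "Vital sign assessments, triplicate ECG recording".

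**The readings.** For Day 1 vital signs, note b of the Schedule of Activities says "To be collected predose, and at 0.25, 0.5, 1, 2, 8 hours postdose", with a window of 5 minutes either side up to 2 hours. For ECGs, note c says "Triplicate at the following timepoints: predose (within 1 hour), and at 90 minutes", with 15 minutes either side, and then 8 hours. SAP 6.7.1 restates the same ECG times.

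**The analysis.** Among the ECG findings, SAP 6.7.1 plans "The proportion of patients obtaining a heart rate change from baseline > 25% decrease resulting in a heart rate < 50 beats per minute", and the mirror category of a rise of more than 25% to above 100 bpm. SAP 6.7.3 lists blood pressure, temperature, "heart rate (beats/min), and respiration (per/minute) for each protocol specified timepoint", and stops there. It gives no cut-off for heart rate, and the SAP has no event category for blood pressure in any section.

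**What else covers the vital signs.** SAP 6.7 summarizes them as values and as change from baseline at each protocol time. SAP 6 includes the minimum and maximum and lists all eCRF data. Protocol 8.2.2 requires a vital-sign abnormality that the investigator judges clinically significant to be recorded as an AE.

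**The concern.** The named risk and the rule that would count it point at different readings. The nonclinical signal is early and transient. The only objective heart-rate rule is applied to measurements that begin an hour after the end of that window, and the measurements inside the window have no rule.

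Safety is the primary objective and the dose cohorts are small, so the natural summary is how many subjects at each dose had a fall of a stated size. As planned, a proportion near zero in the ECG table could be taken as reassurance on the Table 2 risk, although it says nothing about the first hour after dosing. A count for 15 and 30 minutes would then need a cut-off chosen with the data in view, or would rest on the judgement of investigators who are unmasked (Protocol 6.3).

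**Working it through.** The plan states no figure to reproduce here: SAP 6 specifies descriptive summaries only. The check compares times and then runs the SAP's rule on assumed profiles.

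**1. Which readings fall in the 15-30 minute window** (nominal Day 1 post-dose times, Schedule of Activities)

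| Source | Post-dose times (min) | In window | Event category in SAP |
|---|---|---|---|
| Vital signs | 15, 30, 60, 120, 480 | 2 of 5 | None |
| ECG | 90, 480 | 0 of 2 | Heart rate, both directions |

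Earliest in-window ECG: 90 - 15 = 75 minutes. That is 75 - 30 = 45 minutes after the window closes and 75 - 15 = 60 minutes after it opens.

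**2. What the rule requires.** With baseline heart rate b, an event needs a reading below both 0.75b and 50 bpm. The two limits meet at b = 50/0.75 = 66.7 bpm; above that, the 50 bpm limit governs. A 35% fall therefore counts only if 0.65b < 50, that is b below 76.9 bpm. From a baseline of 80 it reaches 52 and is not an event at any time point.

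**3. One assumed subject.** Predose 72 bpm; then 48 at 15 minutes, 50 at 30, 66 at 60, 70 at 90 and 72 at 8 hours.
- At 15 minutes: (72 - 48)/72 = 33.3%, and 48 < 50, so the rule is met.
- At 30 minutes: (72 - 50)/72 = 30.6%, but 50 is not below 50, so it is not met.
- At the 90-minute ECG: (72 - 70)/72 = 2.8%, so it is not met.

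The same rule gives an event on vital-sign heart rate and no event on ECG heart rate.

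**4. How slow recovery must be for the ECG to catch the fall.** Assume a 35% fall at 30 minutes that recovers exponentially with half-time T, in a subject whose baseline lets the rule be met. The remaining fall at time t is 0.35 × 2^(-(t - 30)/T).

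| T (min) | Left at 75 min | Left at 90 min |
|---|---|---|
| 10 | 1.5% | 0.5% |
| 20 | 7.4% | 4.4% |
| 30 | 12.4% | 8.75% |

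To be still at 25% requires 2^(-(t - 30)/T) = 0.25/0.35, so T = (t - 30)/log2(1.4) = (t - 30)/0.485. That is about 93 minutes for an ECG at 75 minutes and about 124 minutes for one at 90. Only a prolonged fall would be counted.

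**5. What the mean table would show.** In a 12-subject cohort, one subject falling by 25 bpm moves the mean change by 25/12 = 2.1 bpm. With an assumed SD of change of 8 bpm, the standard error is 8/√12 = 2.3 bpm. The shift is below one standard error whenever the SD exceeds 25/√12 = 7.2 bpm. The minimum would show the most extreme subject, but not how many fell.

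**6. Whether there would be anything to count.** For assumed true rates of a qualifying early fall of 5%, 10% and 20%, the chance of at least one among 12 is 1 - (1 - p)^12 = 46%, 72% and 93%. These are chances that a fall occurs, not that it is overlooked. A fall that resolves before 75 minutes adds zero to the ECG proportion whatever the true rate.

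**The case against.** The strongest reply is that nothing is lost. The 15- and 30-minute readings are collected, summarized as change from baseline with a minimum, and listed by subject. Vital signs enter the escalation review (Protocol 4.1) and the interim listings (SAP 7). A fall judged clinically significant becomes an AE, and TEAE incidence is the primary endpoint (SAP 5.1). All of this stands. A reader might infer that early falls cannot be scored, or that no proportion reflecting a blood-pressure fall is planned; the documents support neither. What remains is that the AE route has no threshold and relies on open-label judgement. SAP 6.7.1 already adds objective categories for ECG findings, which have the same AE route (Protocol 8.2.3).

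A reader might also take the fall to be an expected event. The protocol calls it a potential risk and anticipates none of particular severity from the mechanism. By its own conversion (20 mg/kg in dogs = 667 mg, about 33.3 mg per mg/kg), the effect dose of 30 mg/kg corresponds to about 1000 mg and the no-effect dose of 10 mg/kg to about 333 mg. The 200 mg top planned dose is 20% and 60% of these. Exposure gives less distance. Table 4 projects AUCs at 200 mg of 383 (AMDX-2011P) and 153 (AMDX-2011), against 400 and 182 in male dogs at 20 mg/kg, a dose between the no-effect and effect doses. The C_max comparison is wider: 1070 against 2270, and 350 against 937. Higher doses may also be explored. The risk is neither expected nor negligible.

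Finally, the 20/10 mmHg figure in Protocol 10.4.2 may look like a ready blood-pressure cut-off. It defines orthostatic hypotension on standing or tilt, whereas study readings are taken at supine or semi-reclined rest (Protocol 8.2.2), so it does not transfer. For the same reason, MSA subjects' possible entry on orthostatic hypotension adds little to the argument.

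**Conclusion.** The point holds in a limited form. The one objective heart-rate rule covers none of the readings in the 15-30 minute window, and the readings that do cover it have no event category for heart rate or blood pressure. That follows from the text and needs no assumption. The result is a gap in pre-specification within the primary safety analysis. It is not lost data, and no endpoint or escalation decision in the documents depends on the missing category.

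The size is illustrative. The 35% fall, the recovery half-times, the SD of 8 bpm and the event rates of 5-20% are assumptions, because the documents give no human values. Some falls of that size would also fail the below-50 bpm condition on vital signs. What does not depend on those values is that a fall meeting the rule early and gone before the first ECG is scored as no event. The change is worth making because it costs little and yields a per-dose rate that depends on neither investigator judgement nor a later choice of cut-off.

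**What to change.** Amend SAP 6.7.3 before database lock:

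- Apply the existing heart-rate categories (fall of more than 25% to below 50 bpm; rise of more than 25% to above 100 bpm) to vital-sign heart rate at every post-dose time, including 15 and 30 minutes. Name Day 1 predose as baseline; SAP 6.7 does not say whether screening or predose is meant.
- Pre-specify a categorical summary of resting blood-pressure falls at the same times. The sponsor's clinical team should set the cut-off for resting readings and should not borrow the orthostatic criterion in Protocol 10.4.2.
- Report, by dose, the proportion of subjects meeting each category and each subject's worst post-dose value.

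The ECG categories can stay as they are. The cost is SAP wording and one table from data already collected, with no new visit or measurement. The small downside is that repeated readings will produce some chance flags, so the table should show results by time point as well as the worst value.

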6.7.2 Physical Exam

Complete physical exam at screening includes assessment of height (in/cm), weight (lb/kg) at screening. General appearance, cardiovascular, respiratory, head, eyes, ears, nose, throat, neurologic, abdomen will be assessed on a scale of normal, abnormal (NCS), abnormal (CS), and not done.

6.7.3 Vital Signs

Vital signs assessment include systolic blood pressure (mmHG), diastolic blood pressure (mmHG), temperature (F), heart rate (beats/min), and respiration (per/minute) for each protocol specified timepoint.

6.7.4 Clinical Laboratory Assessments

Clinical laboratory assessments including hematology, chemistry, coagulation, and urinalysis will be summarized by cohort and overall for each protocol specified timepoint.

6.7.5 Intraocular Pressure

Intraocular pressure (mmHG) using contact or non-contact tonometry will be assessed and summarized for both eyes for each protocol specified timepoint.

6.8 Secondary Analysis

The number, diameter, and area of post-injection hyper-fluorescent puncta detected on fundus fluorescence images upon injection of AMDX-2011P that were not present prior to injection will be summed and descriptive statistics will be presented for each study eye per neurodegenerative disease population (e.g PD, ALS, MSA, CAA) and dose levels.

- Detection of α-syn in the retina after AMDX-2011P administration, defined as the number of distinct new spots that are visible to the naked eye post-injection only.
- Detection of TDP-43 in the retina after AMDX-2011P administration, defined as the number of distinct new spots that are visible to the naked eye post-injection only.

- Detection of Amyloid Beta in the retina after AMDX-2011P administration, defined as the number of distinct new spots that are visible to the naked eye post-injection only.
- PK parameters of AMDX-2011P and AMDX-2011 calculated from concentrations in plasma.

Diagnostic test summary statistics will be presented overall. Calculated values will include:

- A true positive diagnosis is defined as detection of hyper-fluorescent puncta on fundus fluorescence imaging that were not present prior to injection of AMDX-2011P.
- A false negative is defined as an eye from a subject with definite diagnosis and no new hyper-fluorescent puncta detected post-injection of AMDX-2011P via fundus fluorescence imaging that were not present prior to injection.

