9 STATISTICAL CONSIDERATIONS

9.1 SAMPLE SIZE DETERMINATION AND STATISTICAL HYPOTHESES

This clinical study is designed to explore safety and preliminary activity of AMDX-2011P. A total sample size of ~36 subjects and assuming approximately 10% subjects are false negative, the study will provide test sensitivity and test specificity of approximately 0.8 for each individual subject population and the pooled populations. The study will enroll up to 36 subjects with confirmed diagnosis of Parkinson's disease, MSA or ALS (approximately 12 subjects); the prevalence of disease is assumed at 0.5 for each individual disease population.

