9.3 STATISTICAL ANALYSES

9.3.1 General Approach

A formal statistical analysis plan (SAP) and data management plan will be developed and finalized before study database lock. The following is a summary of statistical approach:

- Variables used for sample size calculation will be calculated and presented for pooled populations and each subject population.
- All disposition, demographic, baseline characteristic and concomitant medication summaries will be presented by arm.
- Continuous variables: Descriptive statistics will include the number of non-missing values (n), arithmetic mean, standard deviation (SD), median, minimum and maximum

values. 90% Confidence Intervals (CIs), least-square (LS Means) values and Ratio for Geometrics LS means will also be displayed when appropriate.

- Categorical variables: Descriptive statistics will include counts and percentages per category. The denominator in all percentage calculations will be the number of subjects in the relevant analysis population with non-missing data, unless specifically stated otherwise. Percentages will be displayed to one decimal place. Proportions will be displayed to 3 decimal places.

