9.3.3 Analysis of the Secondary Endpoint (Activity)

The number, diameter, and area of post-injection hyper-fluorescent puncta detected on fundus fluorescence images upon injection of AMDX-2011P that were not present prior to injection will be summed and descriptive statistics will be presented for each study eye per cohort.

A positive diagnosis is defined as detection of hyper-fluorescent puncta on fundus fluorescence imaging that were not present prior to injection of AMDX-2011P.

A false negative is defined as an eye from a subject with definite diagnosis and no new hyper-fluorescent puncta detected post-injection of AMDX-2011P via fundus fluorescence imaging that were not present prior to injection.

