9.3.5 Sub-Group Analyses

Each disease will be analyzed as a subgroup in an exploratory manner. Further details will be provided in the SAP.

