3.1 Sample Size Considerations

A total sample size of approximately 36 subjects and assuming approximately 10% subjects are false negative, the sub-study will provide test sensitivity of at least 0.8 for each individual subject population and the pooled populations in protocol AMDX-2011P-101 Version 5.0, Amendment 5.0. The study will enroll approximately 36 subjects with confirmed diagnosis of Parkinson's disease, ALS, or MSA; the prevalence of disease is assumed at 0.75 for pooled population and 0.5 for each individual disease population. For the CAA group, a total sample size of up to 20 subjects with confirmed diagnosis of CAA, and assuming approximately 10% subjects are false negative, the sub-study will provide test sensitivity of approximately 0.8 for the target population in protocol AMDX-2011P-001.

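### SAP 6.8 reports the diagnostic statistics only overall, although the protocol and SAP 3.1 promise sensitivity for each disease population; it also leaves the counting unit and the formula unstated

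*SAP*

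**What the plan says.** **Reporting level.** SAP 6.8 states "Diagnostic test summary statistics will be presented overall". The protocol commits to more. Section 9.3.1 says "Variables used for sample size calculation will be calculated and presented for pooled populations and each subject population", and section 9.1 shows what those variables are: "the study will provide test sensitivity and test specificity of approximately 0.8 for each individual subject population and the pooled populations". Section 9.3.5 adds "Each disease will be analyzed as a subgroup in an exploratory manner" and leaves the details to the SAP, which has no subgroup section. SAP 3.1 repeats the per-population claim: "the sub-study will provide test sensitivity of at least 0.8 for each individual subject population and the pooled populations". SAP 1.1 lists one change from the protocol, the visit window.

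**Definitions.** SAP 6.8 introduces a list of calculated values, but the list holds two definitions and no statistic. One is "A true positive diagnosis is defined as detection of hyper-fluorescent puncta on fundus fluorescence imaging", limited to puncta absent before injection. The other is "A false negative is defined as an eye from a subject with definite diagnosis", with no new puncta after injection. Protocol 9.3.3 has the same false-negative wording, and its counterpart for positives reads "A positive diagnosis is defined as detection of hyper-fluorescent puncta on fundus fluorescence imaging". Neither document gives a sensitivity formula, a unit for positives, or a rule for a subject whose two eyes disagree.

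**The concern.** Sensitivity is the quantity on which both documents rest the sample size, and both state it for each disease. A programmer following SAP 6.8 as written would produce one pooled figure. That figure cannot show whether the per-population 0.8 was met. The tracer is meant to detect α-syn in PD and MSA and TDP-43 in ALS, so there is no reason to expect equal detection across the diseases. Good detection in the largest group could carry the pooled value.

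The second matter is comparability. The planning assumption counts subjects and the analysis counts eyes. Without a unit for positives and a formula, two analysts could report different sensitivities from the same readings, and neither could be set directly against the 10% assumption.

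**Working it through.** **1. Does any other SAP text restore a by-disease result?**
- SAP 6 sets the default for all summaries as cohort and overall. Protocol Table 3 and the table in SAP 3 define the study 101 cohorts by dose, and each cohort may mix PD, MSA and ALS. SAP 3.2 mentions disease status in cohort assignment, but no study 101 cohort is defined by disease.
- The by-disease sentence that opens SAP 6.8 covers the number, diameter and area of puncta, not the diagnostic statistics.
- SAP 6.1 names a disease split for disposition, so the SAP states a split where it wants one.

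No SAP text restores it.

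**2. The plan's own figure.** With false negatives taken as a share of all subjects, sensitivity = 1 − FN/prevalence.
- Each disease (SAP 3.1 prevalence 0.5): 1 − 0.10/0.5 = 0.80.
- Pooled (prevalence 0.75): 1 − 0.10/0.75 = 0.867.

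This reproduces the stated 0.8. If every subject is diseased (prevalence 1), the same formula gives 0.90. The documents never state 0.90 as a sensitivity, so it is used below only as an assumption.

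**3. What a pooled 0.80 allows.** Total 36 (protocol 9.1, SAP 3.1). The ALS count is about 9 in protocol 4.1 and SAP 3, but about 12 in the protocol synopsis and 9.1, so both are shown. The other diseases share one assumed sensitivity, so the split between PD and MSA does not matter.

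ALS sensitivity = (36 × 0.80 − n_other × S_other) / n_ALS

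| S_other (assumed) | 9 ALS, 27 others | 12 ALS, 24 others |
|---|---|---|
| 0.90 | (28.8 − 24.3)/9 = 0.50 | (28.8 − 21.6)/12 = 0.60 |
| 0.80 | (28.8 − 21.6)/9 = 0.80 | (28.8 − 19.2)/12 = 0.80 |

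An example in whole counts, with 18 PD by subtraction (36 − 9 − 9): 18/18 PD, 8/9 MSA and 4/9 ALS give 30/36 = 0.83 pooled, with ALS at 0.44.

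**4. Unit.** Assume 36 subjects: 26 positive in both eyes, 6 in one eye, 4 in neither.
- Subject, positive if either eye is positive: 32/36 = 0.89.
- Eye: (2 × 26 + 6)/72 = 58/72 = 0.81.
- Subject, positive only if both eyes are positive: 26/36 = 0.72.

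**5. Precision once reported by disease.** Exact 90% intervals near the planned 10% false-negative rate, subject as unit:
- 8/9: 0.57 to 0.99
- 11/12: 0.66 to 1.00 (0.996)
- 16/18: 0.69 to 0.98
- pooled 32/36: 0.76 to 0.96

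**The case against.** The consequence is limited. The protocol calls the disease subgroups exploratory, SAP 6 plans no inference, 6.8 already summarizes puncta by disease and dose for each eye, and all eCRF data are listed. All of this stands. It lowers the stakes but does not deliver the sensitivity by population that protocol 9.3.1 promises.

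Per-disease samples are too small to confirm 0.8: even 9/9 has an exact 90% lower limit of 0.05^(1/9) = 0.72. This stands too. It is a reason to print n and an interval, not to print only the pooled value.

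The masking in step 3 depends on the 0.90. If the other diseases sit at exactly the stated 0.80, a pooled 0.80 forces ALS to 0.80. That is correct: masking needs the other diseases to be above 0.80, and the figures are illustrations.

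The eye is the natural unit for a true positive, since 6.8 reports by study eye and a false negative is an eye. That is a fair inference, and it would settle the numerator. The mismatch with the subject-based 10% in SAP 3.1 would remain, as would the missing formula.

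Two stronger readings are tempting.
- A reader might infer that the definite-diagnosis condition inflates sensitivity, because negatives without that grade would drop out while positives stay. This holds only if the word means the recorded grade, which SAP 6.11.1 provides for ALS and CAA alone. PD and MSA subjects could then never be false negatives, which contradicts a 10% false-negative assumption meant for every population. Both documents say enrolled subjects have a confirmed diagnosis, so the entry diagnosis is the likelier meaning, and under it there is no such bias.
- A reader might infer that the overall figure pools the CAA sub-study, which would hide a weak disease further. The documents do not say so, and SAP 3.1 gives CAA its own target. Nothing here rests on it.

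**Conclusion.** The reporting-level conflict is clear from the text: SAP 6.8 delivers less than protocol 9.3.1, protocol 9.3.5 and SAP 3.1 promise, and SAP 1.1 does not declare it. How much a pooled figure could hide is not fixed by the documents. With the other diseases assumed at 0.90, a pooled 0.80 is compatible with ALS at 0.50 (9 subjects) or 0.60 (12 subjects).

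The unit mismatch is a secondary point. In the assumed example one data set gives 0.72 to 0.89 depending on the rule, so the result cannot be compared directly with the 10% assumption. The definite-diagnosis wording needs clarifying, but bias is not established.

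This should be fixed before database lock. It does not touch the primary safety analysis or any formal test.

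**What to change.** In SAP 6.8:
- State sensitivity = TP/(TP + FN), with both terms taken from one set: Imaging Population subjects with the diagnosis required for entry. This replaces the definite-diagnosis condition.
- Use one unit for both terms. The subject, with a stated two-eye rule, matches SAP 3.1. If the eye is kept, state that positives are eyes too, and use an interval that allows for two eyes from one subject.
- Present the result for PD, MSA and ALS separately and pooled for study 101, with CAA apart. Give n each time and preferably an exact 90% interval when the subject is the unit. The interval is an addition, because SAP 6 mentions 90% intervals with continuous variables.

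The definite-diagnosis and eye wording comes from protocol 9.3.3, so record whatever is replaced in SAP 1.1. If pooled-only reporting is intended, declare that there with a reason.

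The cost is SAP wording and a few tables from data already collected, with no new readings. The downside is that per-disease estimates will be imprecise, and some may be lower than the pooled figure.
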